Additionally, this study will estimate the costs and cost-effectiveness of the reinforcement interventions relative to usual care. If they increase the proportion of individuals who transition to re-employment and reduce time to job attainment, reinforcement interventions may be cost-effective and ultimately integrated in the context of unemployment services. Importantly, reinforcement interventions are now being applied nationwide in the context of substance abuse treatment services ([name] et al., in press b) as well as in other health care arenas (National Business Group on Health, 2013). These dissemination experiences bode well for their ultimate adoption in the context of unemployment services, if benefits are found in this study.

Significance

The unemployment rate in the US remains 7.7% (Bureau of Labor Statistics, 2013), and this rate disguises a larger change in employment patterns, in which precarious or impermanent jobs, that encompass a triad of contingent duration of employment, absence of benefits, and reduced compensation, are increasing (Kalleberg et al., 2000). In part because of this trend, our nation is experiencing the highest poverty level since the early 1980s (Danziger et al., 2012), with a 45% increase in food stamp program enrollment between 2009 and 2012 (Tavernise, 2012). Health disparity groups, including racial/ethnic minorities and those with substance use problems, are most impacted by job loss and unemployment.

Recent data from the National Survey on Drug Use and Health (SAMHSA, 2011) indicate that 33.2% of the unemployed binge drink, and 14.8% have an alcohol use disorder, nearly double the rate of employed persons. The loss of a job, especially involuntary job loss, results in substantial financial, family, and personal stress, along with an increase in unstructured time, all of which can impact alcohol use (Forcier, 1988). Most cross-sectional studies have found greater frequency of hazardous drinking in unemployed versus employed samples (Bolton & Rodriguez, 2009; Dooley & Praise, 1998; Khalt et al., 2004; Mulia, et al., 2013). Longitudinal studies likewise demonstrate that loss of employment can result in greater alcohol consumption and problems (Catalano et al., 1993; Claussen, 1999; Davalos et al., 2012; Mossakowski, 2008; Popovici & French, 2013; Thomas et al., 2005), particularly among men (Virtanen et al., 2008; Deb et al., 2011) and individuals with lower educational attainment (Deb et al.,

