During the 12 weeks, if no recordings are made within the hour for 3 consecutive 1-hr prompt windows, RAs will phone participants to inquire about any problems experienced and remind them of the compensation for complying and penalties for non-compliance. Further, if >40% of tests are missed in a week, RAs will phone to remind them that the service will be disconnected (or the \$35 monthly phone service fee forfeited) if they do not submit at least 50% of requested BrAC tests each week. To re-instate service, participants must submit an unprompted breathalyzer test. Phone service will only be reinstated once during weeks 1-12, such that missing >50% of prompts for two weeks during the three month intervention period will result in discontinuation of cell service (or cell phone payments) and BrAC payments throughout the remainder of intervention phase. Individuals who fail to participate in BrAC monitoring will be encouraged to continue with other aspects of study (and non-study) treatment and follow-ups, but they can also decline (see Human Subjects).

Two weeks before the 12-month follow-up, participants will be invited back for a brief re-training on remote BrAC procedures. They will be asked to complete BrACs when prompted for 14 days using similar procedures outlined above (and further detailed below).

Randomization: After completing BL and training, participants will be randomly assigned to a treatment group. A computerized urn randomization program (Stout et al., 1994) will balance participants on AUDIT scores (< or \geq 12), time since last worked for pay (< or \geq 12 months), and gender, variables likely to impact outcomes. Prior to randomizing participants, up to 10 pilot participants will complete a pilot study consent form and study procedures described for Group D below, through month 3 follow-up, for the purpose of monitoring staff on study procedures prior to the randomized trial. Pilot participants may not meet all inclusion or exclusion criteria, with the exception of those relating to safety and loss of benefits.

Group A (n=70; Standard services plus job activity contracting and alcohol monitoring)

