participants will receive standard employment agency services, including access to workshops, trainings, computers, and a case manager. Study participants will also meet with RAs weekly for 12 weeks. During brief ~20 min meetings, RAs will assist participants in selecting 3 specific job-related activities they can accomplish in the upcoming week. A contract will detail activities, with the purpose of breaking goals into more readily achievable components. Examples include: attending a job club, meeting with a case manager or vocational training specialist, making a chart of potential employers and persons within each hiring agency to call about jobs, completing an in-person or online job training sessions, listing questions to ask at an interview, attending a mock job interview, coming to a clinic appointment dressed in an appropriate manner for a job interview, volunteering, completing a resume, filling out a job application, attending a job interview, writing a thank you note to an interviewer, etc. In initial weeks of the study and for low functioning participants throughout, activities may be simple such as handwriting a resume one week, incorporating improvements the next, then typing it, etc. A higher functioning patient may tailor resumes to specific jobs, attend an intensive workshop, and send in 5 job applications in a week. Once a job is obtained, activities may include going to work on time or enrolling in additional workshops to further skills. RAs will review and provide positive verbal feedback (albeit no tangible reinforcer) for each activity completed to equate for attention across conditions and isolate potential benefits of the activity reinforcement conditions explicitly to the tangible reinforcers. At brief weekly meetings, RAs will also obtain TLFB self-reports of drinking and drug use and provide compensation for BrAC tests, as outlined below.

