Research staff will verify the timing and quality of BrAC tests in "real time" (i.e., upon receipt) during the first 5 days of study participation, and thereafter at least once a day on regular workdays. At a set time on standard workdays, RAs will contact participants by text (or phone or email, based on participant's preference) indicating amounts earned for compliance with BrAC tests since the last message (e.g., "Your 2 samples since yesterday were validated. You earned \$4 for submitting those samples, plus a \$26 weekly bonus for a total of \$30. Thank you!"). If a valid BrAC test is not received, the message may state: "Your 9:15 to 10:15pm test last night was not made, so your next possible \$26 bonus will be available next Thursday. Please carry your equipment and complete all requested tests. Thank you!" Earnings will be available as soon as test results are reviewed, or at the weekly visits. Total earnings for submitting all requested samples will average \$552 over 12 weeks.

Group B (n=70; Reinforcement for negative BrACs) participants will receive the same employment agency services, compensation for complying with BrAC tests, and weekly job activity selections in Group A. Additionally, they will receive reinforcement for each BrAC completed within one hour of the prompts that tests alcohol negative (<0.02 g/dL). Specifically, participants will earn 1 draw for each negative BrAC provided, and bonus draws for each full week of negative samples. Bonus draws start at 5 for the first full week of all negative samples, and increase by 2 draws per week when all negative BrACs are submitted up to a maximum of 15 bonus draws per week. Draws possible will be specified during texted communications after a sample is received and verified by the RA, e.g., "You earned 1 draw because your BrAC is negative, and your 9 bonus draws for 3 weeks in a row of negative samples are possible by Thursday. You also earned \$2 for testing, and your \$26 testing bonus is possible on Friday."

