Economic Evaluation. If primary aims are supported, we will conduct cost-effectiveness analyses.

These interventions can be costly, and not only must costs of reinforcers be included, but so must administration costs, which include staff time for managing and delivering reinforcers. Despite costs, these interventions may provide benefits to society in terms of increased productivity and reduced healthcare service utilization (hospitalizations, ER visits). This study will estimate costs of these reinforcement interventions and determine their net benefit in terms of improving both drinking and employment outcomes.

a. Comprehensive administrative costs of interventions will be quantified (Olmstead et al, 2007abc; Rosenheck et al, 1995; Sindelar et al. 2007ab), including costs of prizes, mileage for purchasing them, BrAC testing and management (personnel time to arrange and review videos, and cell phones costs in Groups B and D), and setting and verifying job-related activities (Groups C and D only). Costs related exclusively to data collection will not be included (i.e., cell phones and staff salary for collection and viewing BrAC videos when not reinforced in Groups A and C). Costs for usual employment and clinical services, and reimbursement for same when applicable, will be ascertained.

b. General healthcare costs will be estimated by multiplying service units used by average unit costs. In- and out-patient, day hospital, aftercare and emergency room services will be estimated from CT claims data, and nationally from the Market Scan database, which estimates service costs.

c. Societal costs will be obtained on productivity (days worked, earnings, and workdays affected by substance use), automobile crashes (including property damage, injuries, and fatalities), and criminal justice system costs. Participants receiving reinforcement interventions may have reduced societal costs, and the SU collects data on these variables, police contacts, court hearings, and incarceration, along with timing of events that resulted in criminal justice service use so acts occurring before study participation can be separated from those occurring during it in terms of resource utilization. Unit costs of services will be estimated from national reports (Pastore & Maguire, 2003; US Dept. of Justice 2006).

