Net benefits. Resource utilization and cost data will be used to estimate mean net benefit (benefits – costs) per patient in each group from agency and societal perspectives (Drummond et al, 2005; Zarkin et al., 2008). Mean net benefits, and confidence intervals around estimates, then will be calculated by subtracting mean net benefit of reinforcement conditions from standard care. Finally, sensitivity analyses (Olmstead et al., 2007a; Drummond et al., 2005) will determine the robustness of the net benefit to alternative assumptions about a variety of cost parameters (e.g., unit costs of services, reimbursements received).

Cost-effectiveness ratios. If the interventions engender net benefits (as they have been shown to in the context of substance abuse treatment; Lott & Jencius, 2009), then they ought to be adopted. Even in the absence of a net benefit, the incremental cost-effectiveness ratio (ICER) is critical to policy decisions. The ICER is calculated as: (i) incremental costs to (ii) incremental effectiveness (difference between average effectiveness of treatments in terms of days abstinent or employed). Using expert panel recommendations (Gold, 1996; Johannesson, 1996; Weinstein, 1996), we will present traditional ICERs and uncertainty of the ratios (Gold, 1996; O'Brien et al., 1994) and derive a single synthetic measure of multiple indicators of effectiveness, including quality of life (Hargreaves et al., 1997; Rosenheck et al., 1998). We will also conduct acceptability curve analysis to provide policy relevant interpretations (Fenwick et al, 2001,2004; Lothgren & Zethraeus, 2000; Polsky et al., 1997; vanHout et al., 1994). Multiple samples are selected randomly (bootstrapped), with replacement, from the original sample to approximate the larger population. Incremental cost and effectiveness values and ICERs can be calculated for each new sample and compared with theoretical "willingness to pay" values for an outcome, such as days without drinking or days employed. Such analyses inform policy makers in decision-making (Olmstead et al, 2007ab; Sindelar et al, 2007b) and can be conducted with samples even smaller than those herein (Olmstead et al., 2007c,2009; Sindelar et al., 2007a).

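### The economic evaluation charges activity setting, phones and breath-test management only where their own target behaviour is reinforced, while effects are measured against a control that also receives them

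*Combined protocol and SAP*

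**What the plan says.** **Cost rule.** Item a of the Economic Evaluation lists the intervention costs to be counted. Prizes are included, together with breath-test management and "cell phones costs in Groups B and D", and "setting and verifying job-related activities (Groups C and D only". It leaves out, as costs of data collection alone, "cell phones and staff salary for collection and viewing BrAC videos when not reinforced in Groups A and C".

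**What the arms receive.** The control condition is headed "Group A (n=70; Standard services plus job activity contracting and alcohol monitoring". In its weekly meetings "RAs will assist participants in selecting 3 specific job-related activities they can accomplish in the upcoming week". Group B receives the same "compensation for complying with BrAC tests, and weekly job activity selections in Group A". The Group C description says its activity contract works as in A and B, and Group D receives both B and C. The opening summary puts remote breath monitoring in all conditions, and the Compensation paragraph gives every participant a phone or $35 a month.

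**Effect measure and comparator.** The ICER divides incremental costs by "incremental effectiveness (difference between average effectiveness of treatments in terms of days abstinent or employed". The Specific aims promise the "cost-effectiveness of the reinforcement interventions relative to usual care", and the Net benefits paragraph takes differences from standard care.

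**The concern.** A cost-effectiveness ratio needs its numerator and denominator to describe the same comparison. Here the difference in effect between Group C and Group A is the effect of prizes for activities, with the verification attached to them, because both arms set activities every week. The planned cost difference between the same two arms also contains the cost of setting activities. The same happens with phones and breath-test management in B versus A.

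No randomised arm received bare usual care, so the trial cannot supply the effect that would match the package-level cost. The net benefits and acceptability curves use the same costs and inherit the mismatch. The plan intends these results to inform agencies and policy makers on adoption, and to identify the simplest cost-effective approach among the arms.

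**Working it through.** **Step 1. Resources delivered against resources charged**

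| Resource | Delivered in | Charged in |
|---|---|---|
| Weekly activity setting | A, B, C, D | C, D |
| Verification needed to earn draws | C, D | C, D |
| Phone or phone payment | A, B, C, D | B, D |
| Breath-test management | A, B, C, D | B, D |
| Prizes | B, C, D | B, C, D |

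Verification and prizes match. Setting, phones and breath-test management do not.

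**Step 2. Effect on the ratio.** Let P be the incremental cost of what differs between two arms (prizes, their handling, verification where it applies), S the shared cost charged to one arm only, and E the difference in effect. The planned ratio is (P + S)/E and the matched ratio is P/E. On intervention costs they differ by the factor 1 + S/P, and E is unchanged. Each net-benefit difference moves by S dollars.

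**Step 3. The plan's own figures.** The plan states no ICER, unit cost or cost by arm, so only its resource counts can be checked.
- Group C draws: 12 x 9 + (6 + 8 + 10 + 12 + 14 + 7 x 16) = 108 + 162 = 270, as stated.
- Group B draws at exactly 10 tests a week: 120 + (5 + 7 + 9 + 11 + 13 + 7 x 15) = 120 + 150 = 270, against a stated average of 266. The gap is 1.5% and does not matter here; 266 is used below.
- Maximum expected value per draw: (164 x $1 + 35 x $20 + 1 x $100)/500 = $1.928. This gives 270 x 1.928 = $521 for C, 266 x 1.928 = $513 for B and 536 x 1.928 = $1,033 for D.

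**Step 4. Size of S.** Three inputs are assumed and do not stand in the documents: staff at $15-40 per hour, setting taking half to all of the 20-minute session, and 1-5 staff minutes per breath test.
- Setting: 12 x 20 min = 4 h, so 2-4 h per participant. 2 x $15 = $30; 4 x $40 = $160.
- Phone: $35 x 3 months = $105, taking the stated phone payment as its cost.
- Breath-test staff time: 120 tests x 1-5 min = 2-10 h, or $30-400.

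| Contrast | Shared cost charged to one arm only | Relative to maximum expected prize value |
|---|---|---|
| C vs A | setting, $30-160 | 6-31% of $521 |
| B vs A | phone, $105 | about 20% of $513 |
| B vs A | phone and staff time, $135-505 | 26-98% of $513 |
| D vs A | all of these, $165-665 | 16-64% of $1,033 |

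Against the roughly $400 of prizes that the plan calls typical, the C versus A range is 8-40%.

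**Step 5. Comparisons among active arms.** D versus B charges setting to D although B received it. D versus C charges phones and breath-test management to D although C received them. In B versus C each arm is charged for one item that both received. At a common hourly wage w, the smallest net shift is $105 + 2w - 4w = $105 - 2w. At $40 this is $25, so within the assumed range B's cost is overstated relative to C's.

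**The case against.** The strongest defence is perspective. The plan gives a rule for phones and breath tests: costs that arise only from data collection are left out. An agency that adopts breath-test reinforcement must pay for the testing, while one that does not adopt it need not. The plan treats the provider's view as crucial, and a costing in which testing cancels would understate the bill for an agency with no monitoring in place. This stands as a reason to keep the current allocation as a scenario. It does not repair the ratio, because the effects still come from monitored comparators. It also offers nothing for activity setting, which is part of the delivered control condition.

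The sensitivity analyses are open-ended, but the examples given are unit costs and reimbursements. Allocation by arm is not named.

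Several stronger readings are tempting, and the documents do not support them:
- A reader might infer that every reinforced arm is charged for everything. Group C is reinforced and is not charged for phones or breath-test management.
- A reader might infer that the whole quoted cost item is misallocated. Verification is tied to earning draws in C and D and belongs there.
- A reader might infer that monitoring was given to all arms in order to isolate the reinforcers. The plan states that purpose only for reviewing activities and giving verbal feedback.
- A reader might infer that effects are certainly smaller than they would be against usual care. That holds only if contracting or monitoring works by itself, which the documents do not show.
- A reader might infer a larger inflation for C versus A by pairing a high wage with few draws earned and charging the whole meeting to setting. The meetings also cover drinking self-reports and payment for tests, and the wage is not in the plan.

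**Conclusion.** The mismatch is real. For activity setting it is unexplained. For phones and breath-test management it follows from a stated and recognisable choice that still does not match the effect contrast. It affects C versus A (setting), B versus A (phones and breath-test management), D versus A (both), and the comparisons among B, C and D. Against Group A the direction is certain: any positive shared cost raises the numerator.

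The size is not certain. The 6-31% for C versus A depends on the assumed wage and session share, and the staff-time part for B versus A depends on assumed minutes per test. All percentages are relative to prizes alone. Adding verification, purchasing mileage and prize handling to the base would lower them, while prizes earned below the maximum would raise them.

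Reach is limited. The economic evaluation is conditional on support for the primary aims, and no primary outcome is touched. For a package-versus-usual-care question the planned costs are coherent by themselves; the trial lacks the matching effect estimate.

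**What to change.** Prespecify a trial-based ICER and net benefit in which each resource is charged in every arm that receives it. Shared setting, phones and monitoring then cancel. What remains as incremental intervention cost is prizes, prize purchase and handling, draw administration and, in C and D, verification.

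Report the current allocation beside it as a programme-cost scenario for an adopting agency, labelled as such. If setting stays charged to C and D only in that scenario, give the reason. In both versions state that effects are relative to standard services plus contracting and monitoring, and align the usual-care wording in the Specific aims. Record the staff time spent on setting separately from verification and from the rest of the weekly meeting, so that the split need not be assumed.

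The cost is revised wording and one extra costing scenario, with no change to the interventions. The trial-based figure will not represent full programme cost, so neither version should be shown alone.

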This study allows for rigorous determination of costs and benefits of interventions that accrue to unemployment service agencies and society more generally. A provider perspective is crucial because, at least in the immediate future, agencies are unlikely to fund expanded services unless they are cost beneficial. Societal perspectives (ICER analyses) are critical for future policy that might allocate state and federal funding to support reinforcement interventions, as is now being done for substance abuse services ([name] et al., in press b) as well as in other health care arenas (National Business Group on Health, 2013). Only a comprehensive study such as this can address multiple perspectives and extend

them to clinically and socially relevant settings and populations.

Future directions: If the dual reinforcement intervention yields the best outcomes and is cost-effective, then that approach should be adopted clinically. If reinforcing job-related activities alone increases job attainment even without reducing drinking, this approach may be expanded to other unemployed groups, including those without drinking problems; if it fails to improve outcomes, other approaches are needed to improve transition to re-employment. Likewise, reinforcing negative BrACs may only reduce drinking but not improve employment outcomes; this BrAC reinforcement approach then may be useful for other populations with hazardous drinking (e.g., college students, patients in medication trials), but not specifically the unemployed. Regardless of outcomes, this study is likely to guide future research and practice in assisting unemployed persons and hazardous drinkers. Importantly, these groups, both independently and collectively, represent a sizeable proportion of US society, and they experience significant—yet preventable— morbidity and mortality.

Human Subjects

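### On the plain reading, the societal ICER per day employed credits each working day twice, as a cost offset and as the effect

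*Combined protocol and SAP*

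**What the plan says.** All the relevant text is in the Economic Evaluation section of the combined protocol and SAP.

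- **Cost side.** Item c reads "Societal costs will be obtained on productivity (days worked, earnings, and workdays affected by substance use", followed by crash and criminal justice costs. It expects that "Participants receiving reinforcement interventions may have reduced societal costs", so more work acts as a cost offset. The section's opening paragraph also presents productivity as a gain: "these interventions may provide benefits to society in terms of increased productivity and reduced healthcare service utilization".
- **Effect side.** The paragraph on cost-effectiveness ratios defines the ICER as "i) incremental costs to (ii) incremental effectiveness", with effectiveness as the "difference between average effectiveness of treatments in terms of days abstinent or employed". Bootstrapped ICERs are compared with willingness-to-pay "values for an outcome, such as days without drinking or days employed". The plan will also "derive a single synthetic measure of multiple indicators of effectiveness, including quality of life", and the components of that measure are not fixed.
- **Perspective.** The closing paragraph of the section states that "Societal perspectives (ICER analyses) are critical for future policy", which ties the ICER to the societal viewpoint and so to the item c costs.

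No sentence says whether productivity belongs in the numerator when days employed is the effect. Item a does state an exclusion (costs that serve data collection only), so the authors write exclusions down when they intend them. The sensitivity analyses are described for net benefit, with unit costs and reimbursements as examples. None takes productivity out of the ICER.

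**The concern.** An ICER asks what is paid for one more unit of effect. If the effect is a day employed, the value of that day should enter through the willingness-to-pay threshold. If the day's earnings have already been subtracted from cost, the same day is used twice, and the comparison with the threshold favours the intervention.

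The plan gives the ICER weight precisely when there is no net benefit, and it presents the acceptability curves as a guide for policy makers. The Future directions paragraph makes clinical adoption of the combined intervention depend partly on its being cost-effective. A ratio that credits each day twice could support that conclusion when the same data, with each day counted once, would not.

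**Working it through.** **Notation.** dC = incremental intervention cost per participant; dE = extra days employed; w = earnings per day employed; L = willingness to pay per day employed.

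**Inputs from the documents**
- Group C maximum draws: 270 as stated. Check: 12 weeks x 9 draws = 108; bonuses 6 + 8 + 10 + 12 + 14 + 7 x 16 = 162; total 270. Reproduced.
- Group D maximum draws: 536 as stated (266 + 270). The 266 is taken as given. At ten tests a week the bonus schedule gives 120 + 150 = 270, a gap of 4 draws (about $8), which does not matter here.
- Maximum expected value per draw, from the prize bowl: (164 x $1 + 35 x $20 + 1 x $100)/500 = $1.928.
- Maximum expected prize value: Group C 270 x $1.928 = $521; Group D 536 x $1.928 = $1,033.

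**Assumptions.** The documents give no values for w, dE or L. I use w = $50 to $120, dE = 5 to 20 days and L = $80.

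**Formulas**
- ICER, employment counted once: dC/dE.
- ICER with earnings netted from cost: (dC - w x dE)/dE = dC/dE - w.
- Value at threshold L, counted once: L x dE - dC.
- Value at threshold L, earnings netted: (L + w) x dE - dC.
- Net benefit with earnings entered once and nothing else: w x dE - dC.

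**Illustration: dC = $1,033, dE = 10, w = $80, L = $80**
- Net benefit: $800 - $1,033 = -$233.
- Counted once: $1,033/10 = $103 per day, above L, so not cost-effective.
- Earnings netted: ($1,033 - $800)/10 = $23 per day, below L, so apparently cost-effective.
- At the threshold: $800 - $1,033 = -$233 counted once, against $1,600 - $1,033 = +$567 with earnings netted.

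**When the verdict reverses.** There is no net benefit, the once-counted ICER exceeds L, and the netted ICER is below L when dC/(L + w) < dE < the smaller of dC/L and dC/w. For dC = $1,033 and L = $80:
- w = $50: from 1,033/130 = 7.9 to 1,033/80 = 12.9 days.
- w = $80: from 1,033/160 = 6.5 to 12.9 days.
- w = $120: from 1,033/200 = 5.2 to 1,033/120 = 8.6 days.

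For Group C (dC = $521, w = L = $80) the window is 521/160 = 3.25 to 521/80 = 6.5 days.

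**Outside the window (dC = $1,033, w = L = $80).** At dE = 5 the ratios are $207 and $127 per day, both above L. At dE = 20 they are $52 and -$28, and net benefit is already +$567. The conclusion is the same under both counts in each case.

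**The case against.** The strongest reply is that the plan never says the item c costs enter the ICER. The numerator is described only as incremental costs. Item c says what data will be gathered, and the one explicit use of resource and cost data is the net-benefit calculation. Productivity is introduced as a benefit to society, which fits net benefit. The link to the ICER rests on one parenthesis about societal perspectives. The cited expert recommendations, which are not available here, might settle the numerator. And if L were defined as the value of a day employed over and above its earnings, nothing would be counted twice.

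This part stands: double counting is the plain reading, not an explicit statement. It does not remove the point, because the plan neither excludes productivity nor defines L, and the choice could be made after the results are seen.

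Two stronger readings are tempting, and the documents support neither.
- **A false sign, or false dominance.** Suppose dC = $1,033 and earnings are $2,000 (20 days at $100, both assumed). The numerator is -$967, but net benefit with earnings counted once is +$967, so calling the intervention cost-saving to society is correct. Whenever earnings alone turn the numerator negative, w x dE exceeds dC and net benefit on the same items is already positive.
- **A further double count of days worked plus earnings within cost.** One is a quantity and the other a money value. Both are listed as items to collect, and nothing says they will be added.

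The dollar figures are also fairly challenged. Wages and days are assumed. The prize cost takes perfect performance and every prize at its ceiling, while leaving out the staff, testing and verification costs that item a requires. The formula dC/dE - w does not depend on these figures, but the location of the reversal window does, and its limits move in proportion to dC.

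**Conclusion.** The point holds in a limited form. On the plain reading, the ICER per day employed and its acceptability curve net earnings out of cost while counting the same days as the effect. The ratio falls by the full daily earnings w, and each day is credited at L + w instead of L. Within a middle range of effects this makes an intervention with no net benefit look cost-effective: 6.5 to 12.9 extra days for Group D's maximum prize cost at w = L = $80. These dollar and day limits are illustrative.

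The point rests on the item c costs belonging to the societal ICER and on L being the whole value of a day employed. It does not show that the ICER would have the wrong sign or that dominance would be spurious.

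The scope is narrow. The days-abstinent ICER does not count employment twice, and neither does net benefit if productivity is entered once. The synthetic measure is exposed only if it includes employment. The economic evaluation is undertaken only if the primary aims are met, and the efficacy analyses are not affected.

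**What to change.** In the Economic Evaluation section, fix the numerator for each effect measure:
- For the ICER per day employed, its acceptability curve and any synthetic effectiveness measure that includes employment, exclude productivity and earnings from incremental cost.
- Value productivity once, through earnings, in net benefit and, if wanted, in the ICER per day abstinent.
- State whether productivity is a benefit or a negative cost in the net-benefit calculation, since the section now describes it both ways.

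This is a wording change that uses data already planned, and it should be settled before results are seen. The price is a less favourable employment ICER.
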